5.2.4 Handling of Withdrawals and Discontinuation of Treatment

The primary reason for withdrawal from this study will be recorded on the Study Status data collection form. Subjects will be encouraged to complete the Early Termination Visit. The Early Termination Visit procedures are listed in Section 7.3.

Although subjects are free to withdraw at any time or may be withdrawn by the site principal investigator or appropriate sub-investigator at any time (see Section 5.2.3), those subjects who receive only one dose of study vaccine will be encouraged to remain in this study for follow-up safety assessments (may be conducted by phone call/electronic communication (e.g., email, text message) rather than in person) continuing through approximately 12 months after their last study vaccination. These subjects will also be encouraged to provide a venous blood sample for serological assessment (HAI and Neut antibody assays) at approximately 28 days after their last study vaccination. Collection of venous blood samples for systems biology studies will be obtained at serial time points indicated per the study schedule, if possible. See the protocol-specific Manual of Procedures (MOP) for alternate follow-up requirements.

Every attempt will be made to follow all adverse events, including solicited injection site and systemic reactions, unsolicited non-serious adverse events, serious adverse events, and medically-attended adverse events including new-onset chronic medical conditions and potentially immune-mediated medical conditions, ongoing at the time of early withdrawal through resolution as per applicable collection times defined for the specific type of adverse event.

In the case of subjects who fail to appear for a follow-up safety assessment, extensive effort (i.e., three documented contact attempts via phone calls, e-mails, etc., made on separate occasions and followed by a certified letter) will be made to locate or recall them, or at least to determine their health status. These efforts will be documented in the subject's study records.

Subjects who withdraw, or are withdrawn or terminated from this study, or are lost to follow-up after signing the informed consent form and randomization but before receipt of study vaccine may be replaced. Similarly, subjects in the A/H7N9 study arms who do not receive their second vaccination will be replaced to ensure that at least 10 evaluable subjects per A/H7N9 study arm are included in the analyses.

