6.3.2. Intention-to-Treat Analysis (ITT) Population

The intent-to-treat (ITT) population includes all subjects who received at least one dose of study vaccine and contributed both pre- and at least one post-study vaccination blood samples for serological assessment (HAI or Neut antibody assays) for which valid results were reported.

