6.3.3. Per protocol (PP) Population

The per protocol (PP) population includes all subjects in the ITT subset with the following exclusions:

- Data from all available visits for subjects found to be ineligible at baseline.
- Data from all visits subsequent to major protocol deviations, such as:
 - Second study vaccination not received,
 - Receipt of non-study licensed live vaccine within 30 days before or after each study vaccination,
 - Receipt of non-study licensed inactivated vaccine within 14 days before or after each study vaccination,
 - Receipt of immunosuppressive therapy (e.g., corticosteroids) within 30 days before or after each study vaccination.
 - Data from any visit that occurs substantially out of window. Substantially out of window is defined as any visit that occurred outside of the pre-defined protocol window except for the following visits for which windows will be redefined as:

- Day 36: +4/-4
- Day 57: +7/-4

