6.3.4. The -Omics Analysis Population

The ‘omics analysis population for the -omics (transcriptomics and proteomics) endpoint analyses will include all subjects who received at least one study vaccination and contributed at least one pre- and one post-vaccination sample for ‘omics testing for which valid results were reported. In addition, the following exclusions will be applied:

- post-second dose samples from subjects in Study Arms 2 and 3 that did not receive second vaccination will be excluded.
- samples that were collected substantially out-of-window will be excluded. Substantially out of window is defined as any visit that occurred outside of the pre-defined protocol window except for the following visits for which windows will be redefined as:
 - Day 36: +4/-4
 - Day 57: +7/-4

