8. IMMUNOGENICITY EVALUATION

8.1. Serum Antibody Analysis

All immunogenicity analyses will be conducted for both the ITT and PP analysis populations. For each analysis population (ITT and PP) and serum antibody assay (HAI and Neut), geometric mean titers (GMTs and two-sided 95% confidence interval (CI) based on t-distribution) and percent seroconversion ([n/N (%)] and an exact (Clopper-Pearson) two-sided 95% CI as defined in Section 3.3) will be summarized by study arm and post-vaccination time point (Table 14, Table 15, Table 16, Table 17). GMTs over time will be summarized using time trend plots (Figure 2). Subject-level serum antibody titer responses at Day 29 post-last vaccination for all three study arms will be contrasted using bar plots (Figure 3). Differences between the treatments will be evaluated at Day 29 post-last dose using two-sided t-tests adjusting for unequal variance if necessary using a standard t-test or Welch's t-test (Table 18, Table 19, Table 20, Table 21). The decision on whether to adjust for unequal variance will be based on inspection of variances for the three study arms. Differences in seroconversion rates for Day 29 post-last dose will be assessed using a two-sided Fisher's exact test (Table 22, Table 23, Table 24, Table 25). Data listings of HAI and Neut assay results will be provided in Listing 8 sorted by study group, subject ID, and visit.

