14.2.2 Plasma Cytokine/Chemokine Data

Table 26: Fractalkine Concentration by Study Visit Day and Treatment Group in the Intent-to-Treat Population

Time Point	Statistic	Study Arm 1 A/H3N2v, D1 (N=X)	Study Arm 2 A/H7N9 + AS03, D1, 29 (N=X)	Study Arm 3 A/H7N9 + PBS, D1, 29 (N=X)
Day 1 (Pre-Vaccination 1)	n	x	x	x
	Min	x xx	x xx	x xx
	Q1	x x	x.x	x x
	Median (95% CI)	x x (x x - x.x)	x.x (x x - x.x)	x x (x x - x x)
	Q3	x x	x.x	x x
	Max	x xx	x xx	x xx
Day 2 (Post-Vaccination 1)	n	x	x	x
	Min	x xx	x xx	x xx
	Q1	x x	x.x	x x
	Median (95% CI)	x x (x x - x.x)	x.x (x x - x.x)	x x (x x - x x)
	Q3	x x	x.x	x x
	Max	x xx	x xx	x xx
Day 4 (Post-Vaccination 1)	n	x	x	x
	Min	x xx	x xx	x xx
	Q1	x x	x.x	x x
	Median (95% CI)	x x (x x - x.x)	x.x (x x - x.x)	x x (x x - x x)
	Q3	x x	x.x	x x
	Max	x xx	x xx	x xx
Day 8 (Post-Vaccination 1)	n	x	n/a	n/a
	Min	x xx	n/a	n/a
	Q1	x x	n/a	n/a
	Median (95% CI)	x x (x x - x.x)	n/a	n/a
	Q3	x x	n/a	n/a

Time Point	Statistic	Study Arm 1 A/H3N2v, D1 (N=X)	Study Arm 2 A/H7N9 + AS03, D1, 29 (N=X)	Study Arm 3 A/H7N9 + PBS, D1, 29 (N=X)
	Max	x xx	n/a	n/a
Day 29 (Post-Vaccination 1)	n	n/a	x	x
	Min	n/a	x xx	x xx
	Q1	n/a	x.x	x x
	Median (95% CI)	n/a	x.x (x x - x.x)	x x (x x - x x)
	Q3	n/a	x.x	x x
	Max	n/a	x xx	x xx
Day 2 (Post-Vaccination 2)	n	n/a	x	x
	Min	n/a	x xx	x xx
	Q1	n/a	x.x	x x
	Median (95% CI)	n/a	x.x (x x - x.x)	x x (x x - x x)
	Q3	n/a	x.x	x x
	Max	n/a	x xx	x xx
Day 4 (Post-Vaccination 2)	n	n/a	x	x
	Min	n/a	x xx	x xx
	Q1	n/a	x.x	x x
	Median (95% CI)	n/a	x.x (x x - x.x)	x x (x x - x x)
	Q3	n/a	x.x	x x
	Max	n/a	x xx	x xx
Day 8 (Post-Vaccination 2)	n	n/a	x	x
	Min	n/a	x xx	x xx
	Q1	n/a	x.x	x x
	Median (95% CI)	n/a	x.x (x x - x.x)	x x (x x - x x)
	Q3	n/a	x.x	x x
	Max	n/a	x xx	x xx

Time Point	Statistic	Study Arm 1 A/H3N2v, D1 (N=X)	Study Arm 2 A/H7N9 + AS03, D1, 29 (N=X)	Study Arm 3 A/H7N9 + PBS, D1, 29 (N=X)
N= Number of subjects in the Intent-to-Treat analysis population n= Number of subjects with valid results Min=Minimum Q1= First quartile Q3=Third quartile Max=Maximum The 95% CI of the median is based on the bootstrap method.				

Tables with similar format:

- Table 27: Fractalkine Concentration by Study Visit Day and Treatment Group in the Per-Protocol Population**
- Table 28: GM-CSF Concentration by Study Visit Day and Treatment Group in the Intent-To-Treat Population**
- Table 29: GM-CSF Concentration by Study Visit Day and Treatment Group in the Per-Protocol Population**

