Interferon-gamma	Day 2 (Post-Vaccination 2) vs. Pre-Vaccination 2	x xxx (x xxx)	n/a	n/a
Interferon-gamma	Day 4 (Post-Vaccination 2) vs. Pre-Vaccination 2	x xxx (x xxx)	n/a	n/a
Interferon-gamma	Day 8 (Post-Vaccination 2) vs. Pre-Vaccination 2	x xxx (x xxx)	n/a	n/a
Colored in blue= p-value < 0.05				

Continue for the remaining cytokine/chemokines IL-1b, IL-2, IL-4, IL-5, IL-6, IL-7, IL-8, IL-10, IL-12p70, IL-13, IL-17A, IL-21, IL-23, ITAC, MIP 1a, MIP1b, MIP3a, TNF-alpha, IP-10, IFNa, IFNb

Table with similar format:

Table 125: Wilcoxon Rank Sum Test Results for Comparing Fold Changes between Study Groups in the Per-Protocol Population

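### Every cytokine table uses a population that requires a valid post-vaccination antibody result, so a subject with valid early cytokine data but no such result drops out of secondary endpoint 1

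*SAP*

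**What the plan says.** SAP 6.3.2 admits to ITT only vaccinated subjects who "contributed both pre- and at least one post-study vaccination blood samples for serological assessment (HAI or Neut antibody assays"), with valid results reported. SAP 6.3.3 builds PP on top of that: "The per protocol (PP) population includes all subjects in the ITT subset with the following exclusions". Protocol 11.5.5 defines both in the same way.

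SAP 8.1 states "All immunogenicity analyses will be conducted for both the ITT and PP analysis populations". That sentence stands in the serum antibody section, and SAP 8.2, on cytokines, names no population. The table shells settle the matter. Table 26 is "Fractalkine Concentration by Study Visit Day and Treatment Group in the Intent-to-Treat Population", its footnote reads "N= Number of subjects in the Intent-to-Treat analysis population", and the last cytokine shell, Table 125, is "Wilcoxon Rank Sum Test Results for Comparing Fold Changes between Study Groups in the Per-Protocol Population".

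SAP 4.5.1 places antibody sera at Day 1, about Day 29 and, in the A/H7N9 arms, Day 57. It places cytokine samples at Days -7, 1, 2 and 4, at Day 8 in the A/H3N2v arm only, and at Days 29, 30, 32 and 36 in the A/H7N9 arms.

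For transcriptomics and proteomics, SAP 6.3.4 uses a set keyed to the assay's own samples: subjects who "received at least one study vaccination and contributed at least one pre- and one post-vaccination sample for" that testing.

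**The concern.** Cytokine and chemokine levels are secondary endpoint 1, and much of their interest lies in the first days after vaccination. Entry to every cytokine summary and test nevertheless depends on a different assay, whose first scheduled post-vaccination sample comes about four weeks later. A subject can have complete, valid Day -7, 1, 2 and 4 cytokine data and still be absent even from the population called ITT. Those data are not missing; a population rule sets them aside.

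Two things are at stake. In arms of 10, one subject is a tenth of the information. And inclusion in an early comparison is made conditional on something that happens after vaccination, which randomisation does not protect.

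**Working it through.** **1. Do all cytokine tables carry the serology condition?** The SAP lists 24 analytes. Concentration and fold change, each in ITT and PP, give 24 × 2 × 2 = 96 tables. The signed-rank and rank-sum results, each in ITT and PP, add 2 × 2 = 4. The total is 100, and Tables 26 to 125 number 125 − 26 + 1 = 100. There is no cytokine table outside ITT and PP.

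**2. Who is dropped?** The population rule set against the schedule:

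| Event | Cytokine sample | Antibody serum |
|---|---|---|
| Day -7 | yes | no |
| Day 1 | yes | yes (baseline) |
| Days 2, 4 | yes | no |
| Day 8 after dose 1 | A/H3N2v arm only | no |
| Early termination, before 28 days after last dose | yes | yes, if attended |
| Day 29 | A/H7N9 arms only | yes |
| Day 57 | no | A/H7N9 arms only |

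Any one valid post-vaccination serum in the last three rows keeps the subject in ITT. The subject dropped is the one who is vaccinated, gives early cytokine blood, and has no valid antibody result afterwards.

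PP adds nothing that would justify the exclusion. For a missed second dose it removes only data from visits after that deviation, so the Day 2 and Day 4 cytokines would otherwise stay.

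**3. What does one such subject cost?** The documents state no power, alpha or effect size, so there is no planned figure to reproduce. The smallest two-sided exact signed-rank p with n pairs is 2/2^n:

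- n = 10: 2/1024 = 0.0020
- n = 9: 2/512 = 0.0039
- n = 8: 2/256 = 0.0078

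The rank-sum test between arms is not limited in this way: its floor, 2/C(n+10, 10), is about 0.00001 for 10 against 10 and 0.00002 for 9 against 10.

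These figures assume no replacement. Protocol 5.2.1 allows vaccinated subjects who are lost to be replaced, and 5.2.4 says A/H7N9 subjects without a second dose will be. With a replacement, the arm analyses 10 when 11 have valid early data, and the floor is 0.0020 instead of 2/2^11 = 0.0010. Either way it doubles for each subject set aside.

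**4. How likely is it?** No rate is given. For an assumed chance p per subject of ending with no post-vaccination serum, the chance of at least one among 30 is 1 − (1 − p)^30:

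| Assumed p | At least one of 30 | Expected number (30p) |
|---|---|---|
| 0.5% | 14% | 0.15 |
| 1% | 26% | 0.3 |
| 2% | 45% | 0.6 |
| 5% | 79% | 1.5 |
| 10% | 96% | 3.0 |

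Nothing in the documents selects a row. Protocol 11.5.7 expects little missing data, which points to the upper rows.

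**The case against.** The strongest reply is that the affected group is very small. A subject who leaves early can still give a serum: Protocol 7.3 lists an HAI and Neut draw at the early termination visit, and SAP 4.5.1 has available sera assayed. An A/H7N9 subject denied the second dose stays in follow-up and is encouraged to give serum about 28 days after the first (Protocol 5.2.4 and 6.3). One who misses Day 29 but attends Day 57 also qualifies. So it would be wrong to infer that everyone lost before Day 29 is dropped. This stands. What remains is that none of these samples is assured; for the early termination visit, "Subjects will be encouraged to complete the Early Termination Visit".

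A reader might also infer that the rule removes strong AS03 reactors and so biases the adjuvant comparison. Protocol 2.3.1 does say that reactions are more frequent with AS03. But the consequence the protocol attaches to a severe reaction is withholding dose 2, not ending follow-up, and no section links reactions to loss without a serum. As a deliberately extreme illustration, if the highest of 10 normally distributed log responses were removed, the median of the remaining nine would be the fifth smallest of the ten, with expectation 0.12 SD below that of all ten. This shows a size, not a likelihood. It is given for the median because the plan uses medians and Wilcoxon tests, not means.

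Nor can one simply say that RNA-Seq already has the right population and cytokines do not. SAP 6.3.4 and the footnotes of Tables 126 and 127 point to the Omics population, but SAP Section 9 assigns the transcriptomics analysis to PP, which carries the same serology condition. Which one governs is unresolved, and the correlation analyses are deferred to addenda outside these documents.

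Finally, exclusions would be visible in Table 9, Listing 5 and Listing 9, and Protocol 11.2 calls the study hypothesis-generating. Both points lower the stakes. Neither gives a reason to key cytokines to an antibody sample.

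**Conclusion.** The point holds as a mismatch between endpoint and population. By the SAP's own definitions and shells, valid early cytokine data are left out of all 100 cytokine tables when the subject has no valid post-vaccination HAI or Neut result. Before Day 29 this touches Days 2 and 4 in all arms and Day 8 only in the A/H3N2v arm.

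The practical effect is probably zero to a few subjects. That is a judgement from the follow-up provisions and the protocol's expectation of little missing data, since no rate is stated. The p-value floors assume exact signed-rank tests without ties or zero differences. The documents do not support a claim that the AS03 comparison will be biased. This is a minor correction, worth making because it is nearly free and keeps secondary-endpoint data that were validly collected.

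**What to change.** In SAP 6.3 add a cytokine analysis set, and cite it in 8.2: all vaccinated subjects with at least one valid pre-vaccination and one valid post-vaccination cytokine result, analysed by randomised arm. Use it in place of ITT in Tables 26 to 125. For the PP versions, apply the existing PP exclusions to this set without the serology condition. Name the population for Figures 4 and 5, which at present name none. There is a precedent: the Omics population is itself an addition in the SAP, since Protocol 11.5.5 lists only Safety, ITT and PP.

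At the same time, reconcile SAP Section 9 (PP) with 6.3.4 and Tables 126 and 127 (Omics population), so that cytokines and RNA-Seq follow the same assay-specific principle. Changing only the cytokine set while RNA-Seq stays on PP could create a difference between two sets that are meant to be correlated.

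The cost is wording and a population flag, with no new data. The one downside is that the cytokine N may differ from the serology N, which a footnote can explain. If every vaccinated subject has valid pre- and post-vaccination results in both assays, the results do not change.

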11.2 Study Hypotheses

This Phase II clinical study is not designed to test a specific hypothesis. Rather it is intended as an exploratory hypothesis-generating study to reveal new insights into how human immune cells respond to influenza A/H7N9 or A/H3N2 vaccination and how AS03 modulates responses to A/H7N9.

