3.2. Endpoints

Primary Endpoints

1. Percentage of subjects achieving seroconversion (defined as either a pre-vaccination HAI titer <1:10 and a post-vaccination HAI titer ≥1:40 or a pre- vaccination HAI titer ≥1:10 and a minimum four-fold rise in post-vaccination HAI antibody titer) at approximately 28 days after the second study vaccination (A/H7N9 vaccine, with and without adjuvant).
2. Percentage of subjects achieving seroconversion at approximately 28 days after the study vaccination with A/H3N2v vaccine.
3. Number of differentially expressed genes based on RNA expression as determined by RNA-Seq analysis, in human immune cells at Days 2, 4, 29, 30, 32, and 36 after study vaccination with AS03-adjuvanted and unadjuvanted A/H7N9 vaccine, as compared to baseline assessments performed prior to vaccination (Days -7, 1, and 29).

Secondary Endpoints

1. Plasma measurement of cytokines and chemokines at each study visit, comparing:
 - a. Post-vaccination time points with pre-vaccination time points by treatment arms.
 - b. AS03-adjuvanted influenza A/H7N9 responses to unadjuvanted influenza A/H7N9 responses.
 - c. Influenza A/H3N2v vaccine to unadjuvanted influenza A/H7N9 vaccine.
 - d. Influenza A/H3N2v vaccine to adjuvanted A/H7N9 vaccine.
2. Serologic response to influenza hemagglutinin:
 - a. Percentage of subjects achieving seroconversion (defined as either a pre-vaccination Neut titer <1:10 and a post-vaccination Neut titer ≥1:40 or a pre-vaccination Neut titer ≥1:10 and a minimum four-fold rise in post-vaccination Neut titer) at approximately 28 days after the second study vaccination (A/H7N9 vaccine, with and without adjuvant).

- b. Percentage of subjects achieving seroconversion at approximately 28 days after the study vaccination with influenza A/H3N2v vaccine.
 - c. Geometric Mean Titers of serum HAI and Neut antibody at baseline (Day -7 and 1) and 28 days after influenza A/H3N2v vaccination.
 - d. Geometric Mean Titers of serum HAI and Neut antibody at baseline (Day -7 and 1), and 28 days after both the first and the second dose of influenza A/H7N9 vaccine (with and without adjuvant).
3. Number of differentially expressed genes based on RNA-Seq analysis in human immune cells at Days 2, 4, and 8 after study vaccination, as compared to baseline assessments (Days -7 and 1) after influenza A/H3N2v vaccine.

Tertiary Endpoints

1. Occurrence of solicited local reactogenicity events within 7 days after each study vaccination.

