4. INVESTIGATIONAL PLAN

4.1. Overall Study Design and Plan

This is a single center, randomized, partially-blinded, Phase II, small, targeted, prospective study in approximately 30 healthy male and non-pregnant female subjects aged 18 to 49 years old, inclusive, designed to evaluate and compare the immunogenicity between an intramuscular monovalent inactivated influenza A/H7N9 virus vaccine manufactured by Sanofi Pasteur given with and without AS03 adjuvant manufactured by GlaxoSmithKline, and an intramuscular unadjuvanted monovalent inactivated influenza A/H3N2v virus vaccine manufactured by Sanofi Pasteur.

This study will use a standard and systems biology approach to assess the human early gene and protein signatures expressed at baseline (approximately Days -7 and 1), and at approximately Days 2, 4, and 8 (A/H3N2v-vaccinated subjects only) after the first study vaccination in each treatment arm as well as at approximately Days 29, 30, 32, and 36 in A/H7N9-vaccinated subjects only. Cellular immunogenicity (systems biology studies) data will be integrated with serologic immunogenicity (HAI and Neut antibody assays) and reactogenicity data to develop a systems model of the human immune response to unadjuvanted monovalent inactivated influenza A/H3N2v virus vaccine and monovalent inactivated influenza A/H7N9 virus vaccine given with and without AS03 adjuvant.

This study will use venous blood samples and subject data collected from a total of thirty vaccinated subjects randomly divided into three equal treatment arms (Table 1). The first treatment arm (n=10) will be vaccinated with one dose of 15 µg of A/H3N2v HA. The second treatment arm (n=10) will be vaccinated with two doses of 3.75 µg of A/H7N9 HA given with AS03 approximately 28 days apart. The third treatment arm (n=10) will be vaccinated with two doses of 3.75 µg of A/H7N9 HA given without AS03 adjuvant approximately 28 days apart. All study vaccinations will be administered intramuscularly.

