6.8. Multiple Comparisons/Multiplicity

No multiple testing adjustments will be carried out for the safety, immunogenicity, and cytokine/chemokine endpoints. For -omics endpoints, the false-discovery rates (FDR) based on the Benjamini-Hochberg procedure as implemented in the R *p.adjust* function will be used to control the false positive rate among significantly differentially expressed genes, proteins, and enriched pathways.

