8.2. Plasma Cytokines/Chemokine Analysis

Pre-first vaccination cytokine/chemokine concentration will be determined using the mean concentrations among pre-vaccination measurements at Day -7 to -1 and Day 1. Cytokine/chemokine concentrations as well as their baseline fold changes will be summarized using minimum, Q1, median, Q3, maximum, and 95% CI of the median (starting with Table 26 and ending with Table 121). The 95% CI of the median concentration and median fold change from baseline will be determined by using the bootstrap method using 1,000 bootstrap replicates and will be visualized using time trend plots (Figure 4) and radar plots (Figure 5). To identify cytokines/chemokines that show a differential response from baseline, a two-sided Wilcoxon signed-rank test will be carried out for each study arm and post-vaccination time point (Table 122, Table 123). Significant differences in fold changes between study arms for shared post-vaccination time points will be evaluated using a Wilcoxon rank-sum test (Table 124, Table 125). Data listings of cytokine/chemokine assay results will be provided as shown in Listing 9 sorted by study group, subject ID, and visit.

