14.2 Immunogenicity Data

14.2.1 Serum Antibody Data

Table 14: Summaries of Hemagglutination Inhibition Antibody Titer by Study Day and Treatment Group in the Intent-to-Treat Population

Time Point	Statistic	Study Arm 1 A/H3N2v, D1 (N=X)	Study Arm 2 A/H7N9 + AS03, D1, 29 (N=X)	Study Arm 3 A/H7N9 + PBS, D1, 29 (N=X)
Day 1 (Pre-Vaccination 1)	n	x	x	x
	GMT (95% CI)	x x (x.x,x x)	x.x (x x,x.x)	x x (x x,x.x)
Day 29 (Post-Vaccination 1)	n	x	x	x
	GMT (95% CI)	x x (x.x,x x)	x.x (x x,x.x)	x x (x x,x.x)
	Seroconversion n/N (%) [95% CI]	xx/xx (xx%) [xx, xx]	xx/xx (xx%) [xx, xx]	xx/xx (xx%) [xx, xx]
Day 29 (Post-Vaccination 2)	n	n/a	x	x
	GMT (95% CI)	n/a	x.x (x x,x.x)	x x (x x,x.x)
	Seroconversion n/N (%) [95% CI]	n/a	xx/xx (xx%) [xx, xx]	xx/xx (xx%) [xx, xx]

N = Number of subjects in the Intent-to-Treat Population
n = Number of subjects with available results
GMT = Geometric mean titer
Seroconversion is defined as having a pre -vaccination titer <1:10 and a post - vaccination titer ≥1:40 or a pre - vaccination titer ≥1:10 and a minimum four -fold rise in post-vaccination antibody titer

Tables with similar format:

Table 15: Summaries of Hemagglutination Inhibition Antibody Titer by Study Day and Treatment Group in the Per-Protocol Population

Table 16: Summaries of Neutralizing Antibody by Study Day and Treatment Group in the Intent-to-Treat Population

Table 17: Summaries of Neutralizing Antibody by Study Day and Treatment Group in the Per-Protocol Population

Table 18: t-Test Results for Comparing Day 29 Post-Last Vaccination Hemagglutination Inhibition Antibody Titer between Treatment Groups in the Intent-to-Treat Population

Statistic	Study Arm 2 A/H7N9 + AS03, D1, 29 (N=X) vs. Study Arm 3 A/H7N9 + PBS, D1, 29 (N=X)	Study Arm 2 A/H7N9 + AS03, D1, 29 (N=X) vs. Study Arm 1 A/H3N2v, D1 (N=X)	Study Arm 3 A/H7N9 + PBS, D1, 29 (N=X) vs. Study Arm 1 A/H3N2v, D1 (N=X)
n	xx	xx	xx
GMT Ratio (95% CI)	x xx (x xx,x xx)	x xx (x xx,x xx)	x.xx (x.xx,x.xx)
t-statistic	x xxx	x.xxx	x xxx
P-value	x xxx	x.xxx	x xxx
N = Number of subjects in the Intent-to-Treat Population n = Number of subjects with available results P-value = two-sided Welch's or standard t-test P-value			

Tables with similar format:

Table 19: t-Test Results for Comparing Day 29 Post-Last Vaccination Hemagglutination Inhibition Antibody Titer Between Treatment Groups in the Per-Protocol Population

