Interferon-gamma	Day 4 (Post-Vaccination 2) vs. Pre-Vaccination 2	n/a	x xxx (x xxx)	x.xxx (x xxx)
Interferon-gamma	Day 8 (Post-Vaccination 2) vs. Pre-Vaccination 2	n/a	x xxx (x xxx)	x.xxx (x xxx)

Colored in blue= p-value < 0.05

Continue for the remaining cytokine/chemokines IL-1b, IL-2, IL-4, IL-5, IL-6, IL-7, IL-8, IL-10, IL-12p70, IL-13, IL-17A, IL-21, IL-23, ITAC, MIP 1a, MIP1b, MIP3a, TNF-alpha, IP-10, IFNa, IFNb

Table with similar format:

Table 123: Wilcoxon Signed-Rank Test Results for Comparing Cytokine/Chemokine Concentrations between Pre- and Post-Vaccination Time Points in the Per-Protocol Population

Table 124: Wilcoxon Rank Sum Test Results for Comparing Fold Changes between Study Groups in the Intent-To-Treat Population

		Study Arm 2 A/H7N9 + AS03, D1, 29 (N=X) vs. Study Arm 3 A/H7N9 + PBS, D1, 29 (N=X)	Study Arm 2 A/H7N9 + AS03, D1, 29 (N=X) vs. Study Arm 1 A/H3N2v, D1 (N=X)	Study Arm 3 A/H7N9 + PBS, D1, 29 (N=X) vs. Study Arm 1 A/H3N2v, D1 (N=X)
Cytokine	Comparison	Wilcoxon Statistic (p-value)	Wilcoxon Statistic (p-value)	Wilcoxon Statistic (p-value)
Fractalkine	Day 2 (Post -Vaccination 1) vs. Pre-Vaccination 1	x xxx (x xxx)	x xxx (x xxx)	x.xxx (x xxx)
Fractalkine	Day 4 (Post-Vaccination 1) vs. Pre-Vaccination 1	x xxx (x xxx)	x xxx (x xxx)	x.xxx (x xxx)
Fractalkine	Day 29 (Post-Vaccination 1) vs. Pre-Vaccination 1	x xxx (x xxx)	n/a	n/a
Fractalkine	Day 2 (Post-Vaccination 2) vs. Pre-Vaccination 2	x xxx (x xxx)	n/a	n/a
Fractalkine	Day 4 (Post-Vaccination 2) vs. Pre-Vaccination 2	x xxx (x xxx)	n/a	n/a
Fractalkine	Day 8 (Post-Vaccination 2) vs. Pre-Vaccination 2	x xxx (x xxx)	n/a	n/a
GM-CSF	Day 2 (Post -Vaccination 1) vs. Pre-Vaccination 1	x xxx (x xxx)	x xxx (x xxx)	x.xxx (x xxx)
GM-CSF	Day 4 (Post-Vaccination 1) vs. Pre-Vaccination 1	x xxx (x xxx)	x xxx (x xxx)	x.xxx (x xxx)
GM-CSF	Day 29 (Post-Vaccination 1) vs. Pre-Vaccination 1	x xxx (x xxx)	n/a	n/a
GM-CSF	Day 2 (Post-Vaccination 2) vs. Pre-Vaccination 2	x xxx (x xxx)	n/a	n/a
GM-CSF	Day 4 (Post-Vaccination 2) vs. Pre-Vaccination 2	x xxx (x xxx)	n/a	n/a
GM-CSF	Day 8 (Post-Vaccination 2) vs. Pre-Vaccination 2	x xxx (x xxx)	n/a	n/a
Interferon-gamma	Day 2 (Post -Vaccination 1) vs. Pre-Vaccination 1	x xxx (x xxx)	x xxx (x xxx)	x.xxx (x xxx)
Interferon-gamma	Day 4 (Post-Vaccination 1) vs. Pre-Vaccination 1	x xxx (x xxx)	x xxx (x xxx)	x.xxx (x xxx)
Interferon-gamma	Day 29 (Post-Vaccination 1) vs. Pre-Vaccination 1	x xxx (x xxx)	n/a	n/a

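### The between-arm cytokine comparisons (secondary endpoints 1b-1d) are planned with a rank-sum statistic and p-value but no between-arm estimate with a confidence interval

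*SAP*

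**What the plan says.** SAP 3.2 lists, as secondary endpoint 1b, the comparison of "AS03-adjuvanted influenza A/H7N9 responses to unadjuvanted influenza A/H7N9 responses". Endpoints 1c and 1d compare A/H3N2v with each A/H7N9 arm. For these contrasts SAP 8.2 says: "Significant differences in fold changes between study arms for shared post-vaccination time points will be evaluated using a Wilcoxon rank-sum test". Protocol 11.5.3 plans the same test, and neither section names an estimator of the difference between arms.

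In SAP Appendix 1, each cell of Table 124 (Table 125 has the same format) is headed "Wilcoxon Statistic (p-value". The footnote reads "Colored in blue= p-value < 0.05". SAP 6.8 adds: "No multiple testing adjustments will be carried out for the safety, immunogenicity, and cytokine/chemokine endpoints".

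SAP 8.2, Tables 74-121 and Figure 4 do plan the median fold change with a bootstrap 95% CI, separately for each arm.

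The antibody tables treat the same arm pairs differently. Table 18 has a row headed "GMT Ratio (95% CI", and Table 22 has an exact odds ratio with a 95% CI.

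Protocol 11.2 states: "This Phase II clinical study is not designed to test a specific hypothesis".

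**The concern.** The AS03 contrast is the reason for having two A/H7N9 arms, and the useful output of a hypothesis-generating study is how large that contrast is and how well it is known. For cytokines the plan supplies a significance flag for the contrast and leaves its size and precision to be pieced together. Dividing one arm's median by the other's gives a rough point estimate, but two separate within-arm intervals do not give an interval for their ratio. With 10 per arm, an uncoloured cell could mean a contrast shown to be close to 1, or one about which the data say little. Table 124 as designed displays the two cases identically.

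**Working it through.** **Inputs from the documents.** Sample size: "thirty vaccinated subjects randomly divided into three equal treatment arms" (SAP 4.1), so 10 per arm. Flag level: 0.05 per test, unadjusted. The sidedness of the rank-sum test is not stated; two-sided is assumed. The plan states no SD, target effect or power for cytokines (SAP 5 gives practical grounds for the sample size), so there is no planned figure to reproduce.

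**Assumptions.** Normal log2 fold changes with equal SD in the two arms, 10 evaluable per arm, no ties. The SDs are chosen only to show a range.

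**How many cells.** Tables 124-125 cover 24 analytes. Arm 2 vs Arm 3 has 6 time points; each of the other two pairs has 2. So 24 × (6 + 2 + 2) = 240 cells per analysis population, of which 24 × 6 = 144 are the AS03 contrast.

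**The exact test.** For 10 vs 10 there are 100 pairwise differences. The exact two-sided test rejects at U ≤ 23 or U ≥ 77, with actual level 0.0433. Inverting it gives the Hodges-Lehmann interval from the 24th to the 77th ordered pairwise difference, with coverage 1 − 0.0433 = 95.7%.

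**Interval width and power.** In simulation (20,000 runs per setting) the median half-width is about 0.98 SD on the log2 scale, so the multiplicative half-width is 2^(0.98 × SD). A true ratio of r is a shift of log2(r)/SD; for r = 2 that is 1/SD.

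| Assumed SD of log2 fold change | 95% interval, either way | Shift for 2-fold (SD units) | Power, 2-fold | Power, 1.5-fold |
|---|---|---|---|---|
| 0.3 | 1.2-fold | 3.33 | about 100% | about 98% |
| 0.5 | 1.4-fold | 2.00 | 98% | 65% |
| 0.8 | 1.7-fold | 1.25 | 71% | 30% |
| 1.0 | 2.0-fold | 1.00 | 51% | 21% |
| 1.5 | 2.8-fold | 0.67 | 26% | 12% |

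**Why the planned cell cannot show precision.** A rank statistic does not change when all log fold changes are multiplied by a constant. One simulated 10 vs 10 data set was analysed at two scales, the second having ten times the log-scale spread of the first:

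- small spread: U = 68, p = 0.19, ratio 1.04 (0.97 to 1.11)
- large spread: U = 68, p = 0.19, ratio 1.55 (0.75 to 2.93)

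The first result limits the contrast to about 11% in either direction. The second is compatible with anything from a 25% reduction to nearly a threefold increase. Table 124 would print the same entry for both.

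**The case against.** The plan is not silent on magnitude. Tables 74-121 put the arms in adjacent columns with quartiles, range, median and a bootstrap interval. Figure 4 adds individual fold changes, and Listing 9 gives every concentration. A reader can see roughly how far apart and how noisy the arms are, and splitting estimates and tests across tables is partly a matter of layout. All of that stands, so it would be wrong to infer that the AS03 effect has no estimate or interval of any kind. What is missing is narrower: an interval for the contrast.

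A reader might also infer that uncoloured cells will be taken as showing no AS03 effect. No passage says so; the blue colouring flags small p-values and sets no decision rule, and the protocol calls the study exploratory.

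A third tempting inference is that most moderate AS03 effects would be missed. That depends on an SD the documents do not give: a 2-fold ratio has 98% power at SD 0.5 and 26% at SD 1.5. For post-first-vaccination fold changes, averaging two baseline samples also reduces noise. An added interval would not raise power in any case; it would show what the data can and cannot exclude.

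Finally, SAP 4.5.1 sets values below the plate-specific LOD to half the LOD, so ties are foreseeable, including fold changes of exactly 1 when both values are imputed at the same LOD. The no-ties exact interval would not then keep its stated coverage, and for a mostly undetectable cytokine the Hodges-Lehmann ratio can collapse to 1. This objection is sound and the fix has to provide for it.

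**Conclusion.** The point holds as a reporting gap. A named secondary contrast has a test but no between-arm estimate with a confidence interval, while the same SAP supplies one for titers and seroconversion. The exploratory label makes an estimate more useful here. The gap does not depend on any SD, because a rank statistic carries no information about scale. Its practical weight does: from an interval of about 1.2-fold either way at SD 0.3 to about 2.8-fold at SD 1.5, assuming normal log2 fold changes, 10 evaluable per arm and no ties. The planned tests remain valid and every endpoint is analysed, so this is an inexpensive improvement and not a flaw in the conclusions the plan can support.

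**What to change.** In SAP 8.2 and Tables 124-125, for each analyte, time point and arm pair:

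- Add beside the p-value the Hodges-Lehmann shift of log2 fold change, back-transformed to a ratio of fold changes, with a 95% CI.
- Use the exact rank-sum interval when there are no ties. When half-LOD imputation creates ties, use a bootstrap or tie-adjusted interval, and name the choice in advance.
- Show the number of values below the LOD in each arm, so that a ratio near 1 for a largely undetectable analyte is not mistaken for a precise null.
- State that the rank-sum test is two-sided, if that is intended; SAP 8.2 says so only for the signed-rank test.

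The cost is one extra column, the LOD counts and a tie rule. The data collected and the planned p-values do not change.
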